4.2. Description of Objectives, Endpoints and Estimands

The primary, secondary and tertiary/exploratory objectives and endpoints assessed (as described in the schedule of activity) to assess the effect of oral Administration of nirmatrelvir/ritonavir in patients with post-COVID-19 symptoms are summarized in the table below.

Objectives	Endpoints	Estimand
Primary	Primary	Primary
To evaluate the effect of oral administration of nirmatrelvir/ritonavir at Day 16 on quality of life	Change from baseline on the EQ-5D-5L VAS scale at day 16	Estimand 1: This estimand is intended to provide a population-level estimate of the mean treatment effect (nirmatrelvir/ritonavir relative to placebo) on a continuous endpoint over time for all randomized/evaluable participants. The difference of Day 16 on EQ-5D-5L VAS scale between the nirmatrelvir/ritonavir and placebo arms in participants with long COVID estimated with a longitudinal analysis that controls for baseline assessment
Secondary	Secondary	Secondary
To evaluate the effect of oral administration of nirmatrelvir/ritonavir in patients with post-COVID-19 symptoms over time on quality of life	Change from baseline on the EQ-5D-5L VAS scale at day 45 and on Day 90	Estimand 1 (see above)

 Version No:

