10.1. Estimands

10.1.1. Primary estimand

• For a given endpoint, the primary estimand will be the population average treatment effect on the change from baseline over time of nirmatrelvir/ritonavir compared to placebo/ritonavir. Measurements after discontinuation of study intervention will be censored and treated as missing data. Missing data due to censoring, study withdrawal or other reasons (e.g., laboratory failure) will have data imputed based on a missing at random (MAR) assumption. Participants with inadequate compliance will have their values used as-is in the analysis. The population-based treatment effect will be the difference in the mean change from baseline in nirmatrelvir/ritonavir arm compared to placebo/ritonavir.

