10.4. Statistical methods

For the primary estimand of the primary endpoint, a linear mixed model (LMM) with subject-specific random intercept will be specified to assess possibles changes over time within and among groups. LMM accounts for both fixed and random effects, can analyze data with repeated measures as well as can handle missing values. Specifically, the LMM will include treatment, time, and time*treatment interaction term as fixed effects, and subject/participant as a random effect. An unstructured correlation matrix will be used. Missing values will be imputed as part of the LMM model assumptions.

No adjustments will be made for multiplicity.

For continuous variables, differences in mean or median between groups will be assessed using Student's t-test (parametric) or Mann-Whitney test (non-parametric) depending on the

 Version No:

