 2.0 Final

 Date:
 10 March 2023

 EudraCT No:
 2022-003855-32

fulfillment of the distributional assumptions of approximation for a normal distribution (Kolmogorov-Smirnov test). Differences in mean or median within groups at Days 16, 45 and 90 with respect to baseline, will be assessed using paired Student's t-test (parametric) or Wilcoxon's signed-rank test (non-parametric) as appropriate.

For continuous primary estimands of secondary endpoints, analysis of covariance (ANCOVA) will be performed to assess changes from baseline on Days 16, or Day 90. Specifically, the ANCOVA will include treatment as fixed effects, and baseline as a covariate.

For dichotomous variables, change in proportions within groups at Days 16, 45 and 90 with respect to baseline (pre-treatment vs post-treatment) will be assessed using McNemar's test.

For categorical variables, frequency distributions will be estimated and compared between the groups using Chi-squared test or the exact Fisher test.

With all baseline demographic and patient's medical history variables a logistic regression model will be adjusted for studying the influence of each of them in the response to treatment. No values will be imputed for missing data, and missing values will not be included in the model.

Sensitivity analyses will be detailed in the SAP prior to database lock and may be include analyses described in the a forementioned alternative study populations.

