10.5. Sample size calculations

The statistical power to detect a 10-unit placebo/ritonavir adjusted improvement from baseline to Day16 (primary endpoint) was estimated using the following assumptions: a 2:1 case-control ratio, nominal significance of alpha=0.05, 1-tailed test and 90 % power. Based on these assumptions, the study population would need to be at least 207 patients. In the study, ~400 participants will be randomized to a) have at least 207 completers to account for 48% dropouts during the execution of the study and b) increase the statistical power for the secondary endpoints of the study that will only be measured in the subset of patients with POTS, and for the secondary endpoints for which the variabilities in the Swedish post-covid patient population are not well documented.

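### The Section 10.4 logistic regression names no covariate-by-treatment term and no definition of response, so fitted as described it shows prognosis and not differential drug effect

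*Protocol*

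**What the plan says.** Section 10.4 says that, with all baseline demographic and medical-history variables, "a logistic regression model will be adjusted for studying the influence of each of them in the response to treatment". Its missing-data rule is explicit: "No values will be imputed for missing data, and missing values will not be included in the model". No treatment term, no interaction and no choice of arm is given.

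The same section does list terms for its other models. For the primary mixed model, "the LMM will include treatment, time, and time*treatment interaction term as fixed effects"; for the ANCOVA, it gives treatment with baseline as covariate.

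In Section 4.2 the primary endpoint is "Change from baseline on the EQ-5D-5L VAS scale at day 16". The secondary endpoints are also changes from baseline, and no responder endpoint or cut-off appears. Section 10.4 mentions tests for dichotomous variables but names no such outcome.

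Under Section 10.1.1, measurements missing through censoring, withdrawal or other causes "will have data imputed based on a missing at random (MAR) assumption"; Section 10.1.2 says the same.

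Section 8.1 limits demography to age, gender and ethnicity. Section 8.2 limits medical history to the COVID-19 history (including vaccination and reinfection) and other relevant diagnoses.

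**The concern.** The stated purpose is to learn which baseline features influence response to the drug. That is a question of effect modification, and it needs the drug-placebo difference to be compared across levels of the feature. A model holding only baseline variables cannot make that comparison. It shows which patients improve, including those who would have improved on placebo/ritonavir.

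This matters because the hypothesis at the end of Section 2 concerns benefit in pre-defined clinical phenotypes, and this is the only analysis in Section 10.4 aimed at who responds. If its coefficients were read according to the stated purpose, ordinary prognostic factors could be taken for predictors of drug benefit.

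Two separate weaknesses cost information. A logistic model needs a binary outcome, so the continuous change would have to be cut at a point that the protocol does not give. And any patient with a missing value is left out.

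**Working it through.** **1. What each version of the model estimates.** Let Y be the VAS change, T = 1 for active, X a baseline covariate, and E(Y) = a + bT + cX + dTX. Then c is prognosis and d is the change in drug effect per unit of X. Under 2:1 randomisation X is independent of T, so the slope on X is:

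- arms pooled, no treatment term: c + (2/3)d
- arms pooled, treatment main effect added: c + (2/3)d
- active arm only: c + d
- interaction term included: d is estimated directly

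With d = 0 the first three return c. A logistic link changes the units but not the argument.

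**2. Inputs for a simulation.** The protocol gives no figure for this model, so there is none to reproduce. From Section 10.5: 400 randomised, 2:1, effect 10 VAS units. Section 10.5 gives no SD. The SD implied by its 207 patients (138 and 69), one-sided 0.05 and 90% power is

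SD = 10 / [(1.645 + 1.282) × √(1/138 + 1/69)] = 10 / (2.926 × 0.1474) ≈ 23.2.

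Assumed: SD 23, response cut-off 10 points, one normally distributed covariate with correlation r = 0.2 to 0.4 to the outcome, and d = 0. There were 600 trials per setting, so a simulated rate has a standard error of up to about 2 points.

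**3. Share of trials with p < 0.05, no missing data.**

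| Test | r = 0 | r = 0.2 | r = 0.3 | r = 0.4 |
|---|---|---|---|---|
| Logistic, covariate, arms pooled | 5.2% | 86.3% | 99.3% | 100% |
| Same, with treatment main effect | 5.0% | 86.5% | 99.5% | 100% |
| Logistic, covariate, active arm only | 5.7% | 73.7% | 98.3% | 100% |
| Logistic, covariate-by-treatment | 5.8% | 5.2% | 3.2% | 7.0% |
| Linear on VAS change, covariate-by-treatment | 6.2% | 6.0% | 3.7% | 5.5% |

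Adding treatment as a main effect changes nothing of substance. Only the interaction rows address the stated question.

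**4. Do the cut or the deleted cases cause the confusion?** With 48% of patients dropped at random (the dropout allowance in Section 10.5), the pooled covariate test falls to 59.3%, 94.0% and 100% for r = 0.2, 0.3 and 0.4. The logistic interaction test, on the dichotomised outcome, stays at 3.3%, 5.2% and 4.3%. So the confusion comes from the missing interaction alone; the other two features cost information.

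**5. Size of the information loss.** For a normal outcome, a cut at the median keeps 2/π = 0.637 of the information, and any other cut keeps less. With 48% dropout, 400 × 0.52 = 208 patients remain before any covariate is missing. The protocol gives no missing rate for baseline items. As assumptions only: 1% missing independently in each of 5 covariates leaves 400 × 0.99^5 ≈ 380 of 400; 5% in each of 20 leaves 400 × 0.95^20 ≈ 143. Demography and medical history are taken once, at screening (Table 1), so nothing in the protocol points to the bad end of that range.

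**The case against.** The strongest reply is that Section 10.4 gives this model one sentence and excludes nothing. Section 10 says that a statistical analysis plan adds detail, and term lists and response cut-offs for an ancillary model are ordinary content there. This stands in part. The protocol names no interaction; it does not rule one out. A reader might infer that the trial will report prognostic factors as predictors of drug response, and the protocol does not support that much. What remains is that the protocol fixes the model type, covariate set, purpose and missing-data rule, and that the model so described does not serve the purpose.

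Second, the 74% to 100% is power to detect a real prognostic association, not an error rate. That is correct. It becomes an error only when the result is read as effect modification, which is how the protocol words the aim.

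Third, a reader might say that the complete-case rule contradicts Section 10.1. It does not. The missing-at-random text governs the estimands, this model is tied to none of them, and the causes listed there are not clearly about baseline covariates. The two approaches are inconsistent in spirit, and no reason for the difference is given.

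Fourth, the protocol never presents this model as the test of the phenotype hypothesis. D-dimer, CRP, ESR and ferritin are laboratory values (Section 8.5.1) and do not clearly enter it. That limits the stakes.

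**Conclusion.** The point holds as a minor one. As described, the logistic model has no defined outcome and no term that could show differential drug effect; its coefficients would be prognostic whether the arms are pooled or only the active arm is used. The algebra in step 1 needs no numerical assumption. The simulated contrast, about 74% to 100% against about 3% to 7%, rests on the assumed SD, cut-off and correlation, and on complete data for 400 patients.

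Dichotomising and case deletion are separate, smaller weaknesses. One might be tempted to count them as further causes of the prognostic-predictive confusion, but step 4 shows that they are not. The primary analysis and the listed endpoints are unaffected.

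**What to change.** Preferred: replace the logistic model with the repeated-measures model for VAS plus a covariate-by-treatment interaction by visit, so that the Day 16 contrast can be read off. Fit one pre-listed factor at a time (for example POTS, post-exertional malaise, inflammatory markers), in the full analysis set with the same missing-at-random handling. Report interaction estimates with confidence intervals, labelled exploratory.

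Alternative: keep the logistic model, define response and its cut-off, say which arms and whether treatment enter, and label the results prognostic only.

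Cost: a few sentences and a few model runs. The downside of the preferred option is modest power. Assume SD 23, complete data on 400 patients and a factor present in 30% (the upper end of the POTS share in Section 2.1). The four cells hold about 80, 40, 187 and 93 patients, and the standard error of the interaction is 23 × √(1/80 + 1/40 + 1/187 + 1/93) ≈ 5.3 points, a 95% interval of about ±10.4. An interaction as large as the whole planned effect of 10 would then reach two-sided significance in only about 47% of trials, since 10/5.32 = 1.88 against 1.96. Hence estimates and intervals, not verdicts.

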10.5. Sample size calculations

The statistical power to detect a 10-unit placebo/ritonavir adjusted improvement from baseline to Day16 (primary endpoint) was estimated using the following assumptions: a 2:1 case-control ratio, nominal significance of alpha=0.05, 1-tailed test and 90 % power. Based on these assumptions, the study population would need to be at least 207 patients. In the study, ~400 participants will be randomized to a) have at least 207 completers to account for 48% dropouts during the execution of the study and b) increase the statistical power for the secondary endpoints of the study that will only be measured in the subset of patients with POTS, and for the secondary endpoints for which the variabilities in the Swedish post-covid patient population are not well documented.

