 2.0 Final

 Date:
 10 March 2023

 EudraCT No:
 2022-003855-32

nearly completely absent in plasma at 24 hours after administration. This suggests that accumulative effects of nirmatrelvir / ritonavir are unlikely. The overall T1/2 was similar in patients with normal and mild renal impairment at ~7 hours. Analysis of urinary excretion data suggests incomplete oral absorption of nirmatrelvir.

Given the differences between acute- and long COVID-19, a prolonged 15 Day treatment period can be motivated by the beneficial observed safety profile of the nirmatrelvir / ritonavir 300/100 mg twice daily dose up to 10 days in safety data [7, 9], and the theoretical need for tissue dissemination of nirmatrelvir / ritonavir to treat potential viral reservoirs.

Hypothesis: Paxlovid® improves health-related quality of life measured with EQ-5D-5L VAS scale vs. placebo/ritonavir in objective and pre-defined clinical phenotypes: POTS, Microvascular dysfunction, inappropriate sinus tachycardia, persistent fever, PEM, fatigue, brain fog, dyspnea, dysfunctional breathing patterns or inflammatory phenotypes (increased D-dimer, CRP, ESR, ferritin)

The purpose of this study is to evaluate the efficacy of nirmatrelvir/ritonavir for the treatment of non-hospitalized patients with post-COVID 19 - a patient group with high unmet medical need. The PROLIFIC study will include non-hospitalized patients only since a) accepted therapies in that group of patients are lacking, b) there are fewer comorbidities, c) there have been indications of persistently ongoing pathology in that patient group, and in some cases viral persistence [5, 6].

3. Benefit-risk evaluation

Specific for this study, there is at present no curative treatment for post-COVID which for the intended study population is a severe condition which affects day to day life with a profound impact on functional capacity and health-related quality of life. It is at present not entirely clear what this condition will contribute to regarding long term organ dysfunction, but several studies indicate long term effects such as the development of diabetes and kidney dysfunction. Any treatment with a curative capacity would be greatly beneficial and outweigh the possible risks.

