 2.0 Final

 Date:
 10 March 2023

 EudraCT No:
 2022-003855-32

9. Reference Safety Information

The Investigator Brochure (IB) for Nirmatrelvir is the reference safety information used for the assessment of whether an AE is expected or not. The reference safety information for Ritonavir is found in document "FDA report NDC 31722-597-30 March9 2023.pdf".

10. Statistics

Detailed methodology for statistical analyses of the data collected in this study is outlined here and further detailed in a Statistical Analysis Plan (SAP), which will be maintained by the KI (Institute of Environmental Medicine).

Statistical hypothesis

- The null hypothesis (H0) is that there is no placebo-adjusted difference in EQ-5D-5L between nirmatrelvir/ritonavir and placebo/ritonavir at Day 16.
- The alternative hypothesis (H1) is that there is a placebo-adjusted difference in EQ-5D-5L between nirmatrelvir/ritonavir and placebo/ritonavir at Day16.

Provided the primary endpoint shows positive signal for H1, additional endpoints will be tested including:

• Sustained EQ5D difference at Day 45 and Day 90.

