10.6. Interim analysis

Interim analysis (IA) will be performed at least once while the study is on-going. This review will include an assessment of the observed safety and observed (versus assumed) variability for the primary endpoint (i.e., EQ-5D-5L VAS) as well as key secondary endpoints hemodynamic response and fever, which is only completed in patients with POTS. The planned IA is proposed after at least 50% of the total planned randomized subjects (i.e., approximately 200 subjects), complete through at least one-third of the total duration of the study. Interim analysis results may be used for conducting a sample size re-estimation, and internal decisions using probability of technical success techniques of the trial (which is not impacting the alpha level). Before any interim analysis is instigated, the details of the objectives, decision criteria, dissemination plan, and method of maintaining the study blind as

 Version No:

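### The Day 16 alternative hypothesis has no direction, but the sample size uses a one-tailed 5% test, so the primary success rule is ambiguous

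*Protocol*

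**What the plan says.** The protocol describes the primary Day 16 comparison in several places.

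- **Section 10, Statistical hypothesis.** The null is no placebo-adjusted difference at Day 16. The alternative is that "there is a placebo-adjusted difference in EQ-5D-5L between nirmatrelvir/ritonavir and placebo/ritonavir at Day16". Neither names a direction. EQ-5D testing at Days 45 and 90 then follows on a condition: "Provided the primary endpoint shows positive signal for H1".
- **Section 10.5.** The size is set to detect a 10-unit improvement with 2:1 allocation and "nominal significance of alpha=0.05, 1-tailed test and 90 % power". This gives at least 207 patients. About 400 are randomised, in part to "have at least 207 completers to account for 48% dropouts during the execution of the study".
- **Section 10.4.** This gives the mixed model for the primary endpoint, but no sidedness, significance level or confidence level.
- **Section 2.3, hypothesis.** The drug "improves health-related quality of life measured with EQ-5D-5L VAS scale vs. placebo/ritonavir" in predefined phenotypes, which is directional wording.
- **Section 4.2.** The primary effect is "estimated with a longitudinal analysis that controls for baseline assessment".
- **Section 10.6.** The interim reviews "observed (versus assumed) variability for the primary endpoint", and "Interim analysis results may be used for conducting a sample size re-estimation".

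No SD for the EQ-5D-5L VAS is given anywhere in the protocol.

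**The concern.** A one-tailed 5% test is not the conventional 5% test of an alternative without direction. The formal hypotheses point to a two-sided test and the sample size to a one-tailed test, and no other section settles it. A statistical analysis plan could follow only one of the two.

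Three things depend on the answer:

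1. **The primary claim.** A one-tailed p-value between 0.025 and 0.05 is a success under section 10.5, but not under a two-sided 5% test of the section 10 hypotheses.
2. **The later tests.** Testing at Days 45 and 90 is conditional on the Day 16 result, so the ambiguity carries forward.
3. **The interim.** A re-estimation that compares observed with assumed variability needs the assumed SD and one agreed sidedness.

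**Working it through.** **Inputs.** From section 10.5: difference 10, allocation 2:1 (138 v 69 at N = 207), alpha 0.05 one-tailed, power 90%, N = 207, about 400 randomised, 48% dropout. The SD is not stated and has to be back-solved. I assume a two-sample t-test on change, with N in multiples of 3.

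**1. Dropout arithmetic.** 1 − 207/400 = 48.25%, and 207/(1 − 0.48) = 398.1, which rounds up to 399. The 207, 48% and 400 agree with each other.

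**2. SD implied by 207.** By the normal approximation, SD = 10 / [(z_α + z_0.90) × √(1/69 + 1/138)], where the root is 0.1474.

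- One-tailed: 10 / [(1.645 + 1.282) × 0.1474] = 23.2
- Two-sided: 10 / [(1.960 + 1.282) × 0.1474] = 20.9

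The noncentral t distribution gives 23.10 and 20.83 for exactly 90% power. The SDs for which 207 is the smallest sufficient N are:

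| Rule behind 207 | SD range | N for 90%, one-tailed 5% | N for 90%, two-sided 5% |
|---|---|---|---|
| One-tailed (as written) | 22.94–23.09 | 207 | 252–255 |
| Two-sided | 20.68–20.82 | 168–171 | 207 |

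Without the SD, 207 can be reproduced under either rule. The number itself does not show which statement is the slip.

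**3. Effect of sidedness alone.** By the normal approximation the ratio of two-sided to one-tailed N at 90% power is (3.2415/2.9264)² = 1.227, whatever the SD. Here 207 × 1.227 = 254, or 255 in multiples of 3. Tolerable loss from 400 is 1 − 255/400 = 36.25%.

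**4. Power and disagreement band at SD 22.94 / 23.10 (noncentral t).** Critical difference = t × SD × √(1/n_active + 1/n_control). At N = 207 and SD 23.10 the standard error is 3.406. The one-tailed threshold is 1.652 × 3.406 = 5.63 and the two-sided threshold is 1.972 × 3.406 = 6.72.

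| Evaluable N | Two-sided power | One-tailed threshold | Two-sided threshold |
|---|---|---|---|
| 207 | 0.837 / 0.832 | 5.59 / 5.63 | 6.67 / 6.72 |
| 300 | 0.944 / 0.941 | 4.64 / 4.67 | 5.53 / 5.57 |
| 400 | 0.984 / 0.983 | 4.01 / 4.04 | 4.79 / 4.82 |

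An observed difference between the two thresholds is positive under one rule and negative under the other.

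**5. Credit for baseline control (section 4.2).** Suppose the SD of about 23 is the SD of change, with equal variances at baseline and Day 16 and correlation r. The residual SD is then SD × √((1 + r)/2), with N − 3 degrees of freedom.

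| r | Residual SD (SD of change 23.10) | Two-sided power at 207 | N for 90% (SD 22.94 / 23.10) |
|---|---|---|---|
| 0.3 | 18.62 | 0.952 | 165 / 168 |
| 0.6 | 20.66 | 0.904 | 204 / 204 |
| 0.7 | 21.30 | 0.887 | 216 / 219 |
| 0.9 | 22.52 | 0.850 | 240 / 243 |

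If 23 is already a residual SD, no further credit is due and 255 stands. The 255 and 36% are therefore the conservative end.

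**The case against.** The strongest reply is that the protocol declares only one alpha and one sidedness: 0.05, one-tailed, in section 10.5. No section states a two-sided 5% or one-sided 2.5% test, so the 2.5% comes from convention. Most of the surrounding wording is also directional. Section 10.5 speaks of improvement, section 10 of a positive signal, and section 2.3 of improving quality of life. On this view section 10 is merely loosely worded, and the SD of 20.7 to 20.8 has no support in the text. Further, test levels normally belong in the statistical analysis plan, and section 10.6 already requires interim objectives and decision criteria to be documented and approved beforehand.

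Some of this stands. The directional reading has more wording behind it, the missing level in section 10.4 is no defect in itself, and the lower SD is only a possibility. The table by correlation also assumes equal variances, which entry restricted to VAS below 50 makes doubtful, and the model in section 10.4 lists no baseline covariate.

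The contradiction remains. The formal alternative has no direction, and the positive signal is defined by reference to that alternative. Deferral to another document does not reconcile two conflicting statements in this one. The interim documentation rule covers re-estimation, not the final success criterion.

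**Conclusion.** The concern holds. Sections 10 and 10.5 conflict on the sidedness of the primary Day 16 test, and the stated 207, 90% and 48% are tied to the one-tailed version only.

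The consequence is moderate. If the SD is about 23, with no credit for baseline adjustment, the change to a two-sided rule reduces the tolerable loss of Day 16 data from 48% to about 36%. Two-sided power falls to 83–84% only if the full 48%, which is stated for the whole study, is already missing at Day 16. The rules disagree over a band of about one VAS point: 5.6–6.7 at 207 evaluable, 4.6–5.6 at 300 and 4.0–4.8 at 400. If the SD was 20.7 to 20.8, 207 is already the two-sided size.

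This does not show that 207 was miscalculated or that the trial is underpowered. It should be fixed because it concerns the primary success rule and the gate to later testing.

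**What to change.** Before the interim analysis and any re-estimation, make sections 10 and 10.5 agree and state the SD used in 10.5. Either route is workable.

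- **(a) Two-sided.** Keep the hypotheses, state a two-sided 5% primary test with a 95% confidence interval, and restate section 10.5. With an SD of about 23 it would give about 255 evaluable at Day 16 for 90% power, with 400 randomised tolerating about 36% loss of Day 16 data. With an SD of 20.7 to 20.8, 207 and 48% stay and only the one-tailed label is corrected.
- **(b) One-sided.** Rewrite the hypotheses with a direction: mean change at Day 16 not greater, against greater, on nirmatrelvir/ritonavir. Declare a one-sided 5% error rate for claiming benefit. Then 207, 90% and 48% stand as stated.

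Use the same sidedness in any re-estimation under section 10.6.

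The cost is a few sentences, with no added patients, visits or endpoints and no change to 400. Route (a) halves the error rate for claiming benefit relative to the one-tailed text and, at an SD of about 23, lowers the stated dropout tolerance. Route (b) commits the protocol openly to a 5% error rate for claiming benefit. Sidedness is not among the examples of substantial change in section 13, so the sponsor should judge whether the correction needs an approved amendment.
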